#### **D. PARTICIPANTS**

## D.1 RCT Participants (N=400)

## Inclusion criteria:

- Living in Mantapala refugee settlement (i.e., Congolese refugee) or (Zambian) member of neighboring host community
- Age ≥15
- Unhealthy alcohol use based on standard cut-off scores of the ACASI-based Alcohol Use Disorders Identification Test (AUDIT) (≥ 8 for men and ≥ 4 for women). The focus on unhealthy alcohol use as the primary inclusion criterion is due to preliminary research in Mantapala suggesting that alcohol is the main substance of concern and other drug use almost exclusively co-occurs with alcohol use.

## Exclusion criteria:

- Severe psychiatric illness, high suicide risk (based on recent attempts and/or ideation with intent and plan), and/or current severe AOD withdrawal that would necessitate immediate referral for psychiatric services
- Inability or unwillingness to provide informed consent

D.2 Implementation Study Participants (N=60; including 30 SBIRT participants from the RCT; 15 CETA-BI/CETA counselors and 15 humanitarian policy/program officials)

## Inclusion criteria:

 Participated in the RCT and received SBIRT, was an SBIRT counselor, or is a humanitarian policy or program official whose position has relevance for the implementation of SBIRT in humanitarian settings

## Exclusion criteria:

• Inability or unwillingness to provide informed consent.

D.3 Exit interviews exploring factors that influence self-reported alcohol and other drug use (n=30; 15 per arm)

#### Inclusion criteria:

- Participant enrolled in RCT (see D.1)
- Completed the 12-month follow-up within the last month

### Exclusion criteria:

• Inability or unwillingness to provide informed consent.

## **E. PROCEDURES**

## E.1 Procedures for RCT

### E.1a Recruitment

The trial will feature several recruitment strategies. First, community meetings will take place at each of the 20 settlement blocks/administrative units and in the surrounding host community. At these meetings we will describe the study in detail and also answer questions and any concerns that community members have. We will provide information on times and places in the community where interested individuals can meet privately with research staff to learn more about the study. Second, we will ask providers within the settlement health clinics and protection programs as well as community leaders to introduce the study to individuals who they believe may have unhealthy alcohol or other drug use. We will provide them with a recruitment script for this purpose. Interested individuals will be given the contact information of the research team to schedule a time to receive more information and also will be able to provide their own contact information if they want so that the research team can contact the individual.

These recruitment strategies ensure that only potential participants who have expressed interest in hearing more about the study (at the community meetings, to a community leader, or to a provider at a health clinic or protection program) will be in contact with the study team.

Recruitment activities will be conducted by the Zambia-based team at WiLDAF and CARE Zambia. Columbia investigators will not be involved in the recruitment process and will not interact directly with potential study participants.

# E.1b Informed Consent

Interested potential participants will meet privately with a trained WiLDAF research assistant (RA) within a secure, private study location in Mantapala settlement and the RA will provide additional detailed information about the study. All participants will provide verbal informed consent/assent as with our previous studies in Zambia (including AAAT1592, which was also conducted in Mantapala) given the sensitivity of signing documents and the increased risk this has for a breach of confidentiality. The Informed Consent Process will begin with a concise and focused presentation of the key information about the research study. The RA will review the study information sheet with the potential participant, which includes information on study purpose, study procedures, risks/benefits, and voluntary participation. All RAs will be trained in human subjects research ethics using the Johns Hopkins

Institutional Review Board field guide, which has been previously used to train research staff working in humanitarian settings.

Consents will be available in English and in Bemba, which is the most widely spoken language among Congolese refugees in Zambia and by the host community. In our previous study in Mantapala, we found that some participants prefer speaking Swahili at times: we will also have an onsite translator/interpreter for participants who may also want to speak Swahili. We will require verbal parental/caregiver permission for participants who are 15, 16 or 17 years of age per Zambian law. Permission will be obtained separately from the adolescent before obtaining verbal informed assent. Informed assent with participants who are 15-17 years of age will be obtained in private without the parent/caregiver present. All potential participants will have the opportunity to discuss the information. This Informed Consent Process presents information in sufficient detail relating to the research study. Consent will be obtained for all study activities (screening, baseline, interventions, follow-up, and implementation interview).

Columbia investigators will not be involved in the consent process and will not interact directly with study participants.

## E.1c Screening

Participants who provide informed consent will complete a brief demographics questionnaire and the Alcohol Use Disorders Identification Test (AUDIT),  $^{20}$  which is a 10-item validated screening tool for unhealthy alcohol use. These measures will be administered through audio computer assisted self-interviewing (ACASI) and available in English and Bemba. The participant will self-complete the measures with the RA nearby in case the participant has any questions. ACASI will automatically calculate the total AUDIT score, which will inform the RA if the participant is eligible for the trial based on the alcohol criterion ( $\geq 8$  for men and  $\geq 4$  for women). Participants who are ineligible for the trial will be thanked for their time and provided with a list of relevant programs and services for mental health in Mantapala settlement and the surrounding area. Participants who are eligible will continue with the baseline assessment.

### E.1d Baseline Assessment

The full baseline assessment will include previously translated and piloted in Bemba measures of our secondary mental health and substance use outcomes. These measures include: depression (Center for Epidemiologic Studies-Depression scale; CES-D); generalized anxiety (Generalized Anxiety Disorder-7 scale; GAD-7); trauma symptoms (Harvard Trauma Questionnaire; HTQ; substance use (Alcohol, Smoking, and Substance Involvement Screening Test; ASSIST); and sleep (Sleep Scale for the Medical Outcomes Research Study). We expect the baseline assessment to take approximately one hour to complete (including the Demographics and AUDIT, which are part of the screening).

Research Assistants will be trained to identify signs of acute alcohol withdrawal and severe mental illness. Participants will also be screened for suicidal ideation during the ACASI assessment. If the RA believes that the participants may be ineligible for randomization and enrollment into the trial on any of these criteria, they will contact an on-site study clinical supervisor for assessment. The clinical supervisor will determine if the participant is ineligible based on these criteria and, if so, will assist the participant in accessing immediate services.

### E.1e Randomization and Enrollment into the Trial

Participants who complete the full baseline assessment and are fully eligible for the trial (have met all inclusion and no exclusion criteria) will be randomized and enrolled into the RCT. Randomization will be on a 1:1 basis, stratified by gender and site (Mantapala settlement or host community) and symptom severity (low or moderate/high). Participants will be randomized to SBIRT or treatment as usual (TAU) control. The RA will allocate participants to study conditions using a series of sealed, opaque envelopes. RAs and data analysts will be blinded. Participants will be notified immediately about the result of the randomization.

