# E.1f Interventions

- SBIRT. All participants randomized to SBIRT will receive an on-the-spot alcohol brief intervention (CETA-BI) and be categorized as low or moderate/high severity. Moderate/high severity is defined as one or more of: (a) AUDIT scores indicating moderate-to-severe AUD (≥12 for women; ≥16 among men); (b) meeting validated symptom criteria for depression (≥16 on CES-D),  (c) trauma/anxiety (≥2.5 on HTQ),  (d) substance use (≥27 on ASSIST).  Participants who are low severity will not receive any additional treatment. Participants who are moderate/high severity will be connected to a CETA counselor and will begin full CETA treatment. This will involve approximately 6-12 weekly CETA sessions. CETA sessions will be conducted in a private setting mutually agreed upon by the counselor and participant (this could be in the health clinic or some other community-based setting where the participant feels comfortable). Data collected for these intervention participants will include the Improving Your Health worksheet (during the BI session), the Client Monitoring Form (during CETA sessions) and the Alcohol Timeline Followback (completed at both the BI and subsequent CETA sessions. All of these measures are included in Rascal.
- TAU. In October 2019, Mantapala health workers and supervisors were trained in mhGAP-HIG, which is a mental health service provision guide for use in humanitarian settings; this training was led by staff from United Nations High Commissioner for Refugees. This training did *not* include evidence-based psychological interventions (e.g., CETA). Participants randomized to TAU will be referred to the existing services that exist in the health clinic located in Mantapala refugee settlement. This clinic is staffed by eight clinical staff who provide clinical assessments, primary care, basic counseling, and limited specialized services (e.g., maternal and child care, HIV treatment). More specialized services are referred to the District Hospital in Nchelenge, which is the nearest town approximately 50 kilometers away.

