# E. Ig Follow-up Assessments

Participants will be asked to complete two follow-up study assessments at 6- and 12-months post-baseline. We will ask the participants to complete the same ACASI questionnaire as baseline. We expect these study visits to take approximately one hour. Participants will be eligible to complete these assessments within a +/- one month window around the 6 and 12 month scheduled assessments. If they do not complete the assessment within that window it will be considered a missed visit. Once participants complete the 12-month visit, they will exit the study.

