## E.2 Procedures for Implementation Interviews

### E.2a Recruitment

We will conduct implementation interviews with a subset of participants enrolled in the RCT as well as other relevant stakeholders. Participants in the implementation interviews include participants enrolled in the RCT who received SBIRT (n=30), SBIRT counselors (n=15), or is a humanitarian policymakers or program officials whose position has relevance for the implementation of SBIRT in humanitarian settings (n=15). We will purposively recruit a subset of 30 RCT participants who received SBIRT selected using maximum variation sampling to ensure they represent both refugee and host community members, participants with a range of alcohol and substance use patterns at baseline, and variations in attendance and intervention response. Participants will be invited to complete the implementation interview by the RA at their 6-month follow-up interview. Fifteen SBIRT counselors will be invited by an RA to participate in an implementation interview at the end of their final SBIRT session. We will purposively select counselors to reflect variation in the following characteristics: number of SBIRT and CETA sessions delivered, community membership (refugee vs. host), and competency as identified by the clinical supervisor. Fifteen humanitarian stakeholders (e.g., policymakers and program officials) will be invited to participate in the study interview by a member of our research team throughout the study period. We will select these stakeholders based on their knowledge of the project and the relevance of their role in its implementation.

Recruitment activities will be conducted by the Zambia-based team at WiLDAF and CARE Zambia. Columbia investigators will not be involved in the recruitment process and will not interact directly with potential study participants.

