## E.2b Informed Consent

Trial participants who are selected to complete an implementation interview will be reminded by the RA of the original study consent form (see section E.1b), which includes information about potential participation in the implementation interview. The RA will offer to provide a copy of the consent form for their review, if interested. They will review the study information sheet again with the participant prior to initiating the implementation interview and provide an opportunity for the participant to ask any questions before beginning.

Selected providers and invited humanitarian stakeholders who have not been previously enrolled in the study will meet with a trained WiLDAF RA in a secure, private study location in Mantapala settlement, another secure office, or by phone to review details about the study. All participants will provide verbal informed consent as with our previous studies in Zambia (including AAAT1592, which was also conducted in Mantapala) given the sensitivity of signing documents and the increased risk this has for a breach of confidentiality. Similar to participants enrolled in the trial, the Informed Consent Process will begin with a concise and focused presentation of the key information about the research study. The RA will review the study information sheet with the potential participant, which includes information on study purpose, study procedures, risks/benefits, and voluntary participation. All RAs will be trained in human subjects research ethics using the Johns Hopkins Institutional Review Board field guide, which has been previously used to train research staff working in humanitarian settings.

Consents will be available in English and Bemba. In our previous study in Mantapala, we found that some participants prefer speaking Swahili at times: we will also have an onsite translator/interpreter for participants who may also want to speak Swahili. This Informed Consent Process presents information in

sufficient detail relating to the research study. All potential participants, including the participants already enrolled in the RCT, will have the opportunity to discuss the information.

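### Research assistants are declared blinded, but the written procedures have them allocate participants and invite SBIRT-only interviewees before the primary outcome visit

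*Combined protocol and SAP*

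**What the plan says.** **Allocation.** Section E.1e (Randomization and Enrollment) reads: "The RA will allocate participants to study conditions using a series of sealed, opaque envelopes. RAs and data analysts will be blinded". It adds that the participant learns the result immediately, without naming who tells them. Section E.1f then gives everyone in the SBIRT arm a brief intervention straight away, while TAU participants are referred to the settlement clinic.

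**Implementation interviews.** The recruitment section (E.2a) draws the 30 trial interviewees only from those who received SBIRT. On the invitation it says: "Participants will be invited to complete the implementation interview by the RA at their 6-month follow-up interview". The consent section (E.2b) continues: "Trial participants who are selected to complete an implementation interview will be reminded by the RA of the original study consent form". The interview section (headed E.3c) has an RA from the local partner carry out the interviews, which are about SBIRT.

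**Outcome assessment.** Section F sets the primary outcome as the between-arm difference in AUDIT change from baseline to 12 months. The follow-up section (E.1g) says "We will ask the participants to complete the same ACASI questionnaire as baseline", but not which staff attend. The screening section (E.1c) describes the RA's part in the self-interview: "The participant will self-complete the measures with the RA nearby in case the participant has any questions".

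**Staffing.** Section K describes one group of RAs supervised by two program officers, with daily debriefings. It gives no division of RA duties.

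**The concern.** The blinding sentence has no qualifier, so it claims that every RA is unaware of allocation. Opaque sealed envelopes hide the next assignment until it is made. They do nothing to keep the person who makes it unaware afterwards. The SBIRT-only interview is a separate source of knowledge: inviting, consenting or interviewing someone for it identifies that person's arm, and the invitation comes before the primary endpoint.

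What is at stake is mainly the accuracy of a methods statement. A trial report repeating that RAs were blinded would lead readers to credit a safeguard that the written design does not provide. The secondary risk is that an RA who knows the arm, and is on hand to answer questions during the 12-month self-interview, could influence responses.

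**Working it through.** The plan gives no figure to reproduce on this point. The check sets the sections side by side and then counts the exposure.

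1. **Does the RA who allocates learn the arm?** E.1e assigns allocation to the RA. It does not say who opens the envelope or who informs the participant. Immediate disclosure (E.1e), followed by an immediate brief intervention in one arm and a clinic referral in the other (E.1f), makes knowledge of the arm likely. Nothing in the text prevents it.

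2. **Is there a route that does not depend on the envelope?** Yes. Under E.2a, E.2b and E.3c for the implementation interviews, RAs invite, review consent with, and interview trial participants drawn from the SBIRT arm alone. Taking part in any of these steps reveals the arm.

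3. **Does this come before the primary outcome?** The invitation does. The follow-up section sets the windows: "Participants will be eligible to complete these assessments within a +/- one month window around the 6 and 12 month scheduled assessments". The 6-month visit can therefore fall at months 5 to 7 and the 12-month visit at months 11 to 13. From invitation to primary AUDIT:
   - shortest gap: 11 − 7 = 4 months
   - as scheduled: 12 − 6 = 6 months
   - longest gap: 13 − 5 = 8 months

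   The date of the interview itself is not stated.

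4. **Are RA roles separated anywhere?** No. The consent, screening, baseline, randomization, interview and study management sections all refer to RAs without dividing their duties. E.1g is silent on who attends follow-up. The two recruitment sections do place an RA at the 6-month visit (implementation interviews) and at the 12-month visit (exit interviews).

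5. **Do the exit interviews add to the problem?** No. They cover both arms (15 each) and follow the 12-month assessment.

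6. **How large is the exposure?** With 1:1 randomization, 400 / 2 = 200 per arm.
   - Allocations made by an RA: 400 of 400.
   - Arm-revealing invitations: at least 30 / 200 = 15% of SBIRT, and 0 / 200 = 0% of TAU. Thirty is the planned number of interviews, so more may be invited.
   - Invitees who meet the same RA again at 12 months: not stated, so not calculable.

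**The case against.** The strongest reply is that the text is incomplete, not contradictory. There is more than one RA, so a different person could attend the 12-month visit. The RA could also hand over the envelope unopened, and section B says lay counselors deliver the SBIRT components, so no RA need be present at the brief intervention. On this reading the fault is only that roles are not specified. The interview route concerns about 30 planned participants, and it touches the primary outcome only if the same RA returns at 12 months. The consequence is also slight: AUDIT is self-completed and scored automatically, participants know their arm whatever the RA knows, and analyst blinding is not in question. The sponsor also plans exit interviews in both arms on the accuracy of self-reported use, which bears on the larger threat of reporting bias.

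Much of this stands. Who attends follow-up is indeed unspecified, the brief intervention is supporting evidence only, and the likely bias is small. It does not rescue the blinding sentence. That sentence names RAs as a whole, while other sections give RAs tasks that cannot be done without knowing the arm. An unopened envelope and a different RA at 12 months are both possible, but neither is written, and the SBIRT-only invitation and interview reveal the arm either way. If roles are already separated in the field, writing that down is the remedy.

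**Conclusion.** The concern holds. The unqualified claim that RAs are blinded is inconsistent with the protocol's own allocation and interview procedures, and no section limits the claim to RAs for whom it could be true. It should be fixed, but it does not undermine the randomized comparison.

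The documents give no basis for putting a figure on bias. The judgment that it is probably small assumes that the 12-month self-interview runs as described at screening, with the RA available only for questions. The exposure counts assume equal arms of 200 and invitations limited to the 30 planned interviews, so 15% is a minimum. They describe contact as written and do not show that any RA influenced a response.

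**What to change.** Either of two changes resolves the inconsistency.

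**Option A: separate the roles, using existing staff.**
- E.1e: name someone who does not attend follow-up visits, such as an enrolment-only RA, to open the envelope once the baseline self-interview is complete and eligibility is recorded.
- Implementation interviews (E.2a to E.3c): have someone who will not attend that participant's 12-month visit give the invitation after the 6-month self-interview is finished, review consent, and conduct the interview. Keep the invitee list from RAs who attend 12-month visits.
- E.1g: state that RAs attending the 6- and 12-month visits do not allocate, invite or interview and are not told the arm. Limit the blinding sentence in E.1e to those RAs.

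The cost is protocol wording plus rostering for about 400 envelope openings, at least 30 invitations and 30 interviews. The number of RAs is not given, so feasibility cannot be checked from the documents. Giving the envelopes to the two program officers would mean 400 / 2 = 200 openings each, so an enrolment-only RA is the lighter arrangement. The arm may still leak through the daily debriefings or from participants themselves.

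**Option B: if roles cannot be separated, withdraw the RA blinding claim** from the protocol and reports. State instead that AUDIT is self-completed and scored automatically by ACASI, with an RA nearby for questions. This costs wording only, and it gives up the claimed safeguard.

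Neither option changes the sample size, the treatments or the analysis, and neither alters the fact that participants know their own arm.
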